**Aim 2: Explore secondary physical and mental health outcomes of the study cohorts.**

Primary outcomes will assess participant adherence to the study protocol and satisfaction with the intervention. Secondary outcomes will preliminarily assess the effect of the intervention on clinical care measures (e.g., HbA1c, BMI) and patient-centered outcomes including quality of life. We will identify factors that support or interfere with the uptake and sustained use of the intervention in the diabetes care context to assist in future multi-site, pragmatic, or implementation science trials. We hypothesize that offering mindfulness-based skills will result in improved outcomes and thus would lead to change in clinical practice to incorporate such teachings.

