## **4.0 Enrollment**

We aim to recruit 50 individuals with the goal of at least 20 participants to complete the study (two groups of 10 participants).

**Recruitment Sites:** Diabetes care providers see patients in an outpatient setting at Riley Specialty Care at IU Health Methodist in Indianapolis, Indiana. Additional outreach clinics available for participant recruitment include Riley Specialty Care at Riley Outpatient Center, IU North, Bloomington, Fort Wayne, and South Bend.

**Recruitment Procedures:** Eligible patients will be recruited in one of the following ways: 1) health care providers will identify eligible adolescents during clinic visits, 2) a letter will be mailed to patients referred for prediabetes or type 2 diabetes who have been seen in one of our clinics within the last 12 months, or 3) a member of the research team will call eligible patients. The letter and phone call scripts are provided in separate documents.

**Consent Procedures:** When a family indicates interest, a member of the research team will initiate contact with the parent or guardian at the end of a clinic visit (if time allows) or by phone. The team member will describe the study, assess eligibility, and answer questions. If the adolescent (and guardian) is willing to participate in the study, the consent process and baseline questionnaires will be completed virtually. The consent process will be based in REDCap. If a family declines participation, they will be asked if they would like to complete the study declination form. This will help to understand reason for disinterest in a MBI.

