#### **Intervention:**

The MBI will be conducted in a virtual group setting by Zoom, with a target size of 8-12 participants. Groups may vary in size based on session attendance.

***Mindfulness-based intervention.*** The MBI will follow the Learning to BREATHE (L2B) curriculum. L2B is a manualized 12-week curriculum that teaches a variety of mindfulness skills including breath awareness, body scanning, mindful eating, sitting meditation, loving kindness practice, and mindful movement. Weekly group sessions will last 45-60 minutes. Participants will be invited to engage in daily practice of mindfulness skills (home practice).

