## **8.0 Statistical Considerations**

Anticipated statistics for this study will be a combination of descriptive statistics and quantitative statistics. For our primary outcomes, we will examine retention and acceptance, as assessed by overall program attendance, program acceptability, and qualitative interviews. Descriptive statistics will include sex, ethnicity, and survey results at B, T1, and T2.

This study includes a post-intervention group guided interview at 12-weeks. The facilitator will ask the group for feedback about the intervention with the following questions: 1) What did you like about participating in this study? 2) What did you dislike about participating in this study? 3) What were your expectations from participating in this study? 4) Were those expectations met?

A paired t test will be used to compare variables of an individual at baseline and at the end of the study (pre/post), including HbA1c, BMI, BMI z-score, and survey results.

This is a pilot feasibility study, therefore there are no data currently available to accurately calculate power. There are no similar studies to substitute such data.

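### The paired t test for the secondary pre/post outcomes assumes independent changes, although the intervention is delivered in groups of about 10; if changes correlate within a group, its standard error is too small

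*Combined protocol and SAP*

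**What the plan says.** Under the Intervention heading of Section 5.0, delivery is by live group: "The MBI will be conducted in a virtual group setting by Zoom, with a target size of 8-12 participants". The same paragraph adds: "Groups may vary in size based on session attendance". Section 4.0 sets the size of the study: "We aim to recruit 50 individuals with the goal of at least 20 participants to complete the study (two groups of 10 participants".

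Section 8.0 gives one inferential method: "A paired t test will be used to compare variables of an individual at baseline and at the end of the study (pre/post". It applies this to HbA1c, BMI, BMI z-score and survey results. On sample size it says: "This is a pilot feasibility study, therefore there are no data currently available to accurately calculate power".

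The tested outcomes are secondary. Section 2.0, Aim 2, says: "Secondary outcomes will preliminarily assess the effect of the intervention on clinical care measures (e.g., HbA1c, BMI) and patient-centered outcomes including quality of life". The primary outcomes are handled separately in Section 8.0: "For our primary outcomes, we will examine retention and acceptance, as assessed by overall program attendance, program acceptability, and qualitative interviews". No test or standard error is specified for them.

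The plan does not mention clustering by group, an ICC, a design effect, a group term in a model, or results by group. It also states no significance level and mentions no confidence intervals.

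**The concern.** A paired t test is a one-sample t test on the individual changes, and its standard error is right only if those changes are independent. Here the members of a group meet weekly for 12 weeks and work together on thoughts, emotions and stress. These topics are close to what the depression, anxiety, stress, mindfulness and emotion-regulation surveys measure. Table 1 refers to recruitment waves, so groups may also differ in calendar period. Some positive correlation of survey changes within a group is therefore plausible.

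With positive correlation, 20 completers in two groups carry less information than 20 independent participants, and the planned p values are too small. The stake is moderate. These comparisons are preliminary, but Section 2.0 says the study is meant to assist future multi-site and implementation trials, and p values from it will be read as a signal.

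**Working it through.** **Plan's own figure.** There is none to reproduce: the plan gives no power, significance level or ICC.

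**Inputs from the documents.** Group size m = 10 (target range 8 to 12); number of groups k = 2; completers n = k × m = 20. If all 50 recruits completed in groups of 10, k = 50/10 = 5.

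**Assumed inputs.** Two-sided nominal 5% test; ICC of the changes 0, 0.01, 0.05 and 0.10; SD of change scaled to 1, since its value does not affect the error rate.

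**Formulas.**
- Design effect: DE = 1 + (m − 1) × ICC.
- Effective sample size: n / DE.
- Ratio of the true to the naive standard error: √[DE × (n − 1) / (n − DE)]. This slightly exceeds √DE because clustering also makes the sample variance too small.

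**Worked case, ICC 0.05.** DE = 1 + 9 × 0.05 = 1.45. Effective n = 20 / 1.45 = 13.8. Ratio = √(1.45 × 19 / 18.55) = 1.22.

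**Type I error.** This comes from simulating 200,000 trials per setting with zero true change and a normal group effect, and testing the changes with the ordinary t test.

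| ICC | DE | Effective n (of 20) | True / naive SE | Type I error, 2 groups of 10 | Type I error, 5 groups of 10 |
|---|---|---|---|---|---|
| 0 | 1.00 | 20.0 | 1.00 | 5.1% | 5.1% |
| 0.01 | 1.09 | 18.3 | 1.05 | 6.0% | 6.1% |
| 0.05 | 1.45 | 13.8 | 1.22 | 10.2% | 10.3% |
| 0.10 | 1.90 | 10.5 | 1.41 | 15.5% | 15.5% |

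The values at ICC 0 are 5% apart from simulation error. Five groups give almost the same inflation as two, so running more groups does not remove the problem. Group size matters somewhat: at ICC 0.05, two groups of 8 give 9.0% and two groups of 12 give 11.4%.

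**Can the data supply the correction?** Hardly. With two groups, a test on group means has 1 degree of freedom and a critical t of 12.71, against 2.09 for the naive test on 19. Even at ICC 0 its 95% half-width is 12.71 × √(1/20) = 2.84 SD, against 2.09 × √(1/20) = 0.47 SD. More groups do not make the ICC itself estimable. In simulation with a true ICC of 0.05, the usual analysis-of-variance estimate was zero or negative in 42% of trials with 4 groups and 38% with 5. Its central 95% range was about −0.10 to 0.30 with 4 groups and −0.09 to 0.27 with 5.

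**Does widening over an assumed ICC work?** Multiplying the naive standard error by √DE (1.04, 1.20 and 1.38) gave a type I error of 5.2%, 5.2% and 5.5% with two groups when the assumed ICC was the true one. In units of the SD of change, the half-width of 0.47 becomes 0.468 × 1.044 = 0.49, 0.468 × 1.204 = 0.56 and 0.468 × 1.378 = 0.65.

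**The case against.** The strongest reply is that the inflation depends wholly on an ICC that nobody has stated. At 0 the test keeps its level, and at 0.01 the excess is about one percentage point. This stands, and it is why the point is conditional.

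The likely sources of correlation are also uneven. Sessions are manualized, scripted and checked for fidelity, so content is common to all groups. A facilitator creates differences between groups only if groups have different facilitators, and the plan does not say whether they do. HbA1c and BMI come from each participant's own clinic appointments. This also stands: one ICC range for every outcome is a convenience, and the upper values are harder to defend for HbA1c and BMI.

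Third, in a single-arm study a pre/post change cannot be attributed to the intervention whether the error rate is 5% or 10%, because time trends, regression to the mean and medication changes remain. This is correct and limits how much the point matters. It does not justify a standard error that may be too small when the remedy is so cheap.

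A reader might go further and infer that the primary results are compromised too, since attendance and satisfaction may also run together within a group. The documents do not support that: Section 8.0 attaches no t test or standard error to those outcomes, so this error cannot enter them.

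**Conclusion.** The point holds in conditional form, for the secondary pre/post comparisons only. Section 8.0 uses a test that needs independent changes, in a design that gives reason to doubt independence, and says nothing about it. For two groups of 10 and a two-sided nominal 5% test, the true standard error is about 1.05, 1.22 and 1.41 times the naive one at ICCs of 0.01, 0.05 and 0.10. The type I error is about 6%, 10% and 15–16%. The ICCs and the 5% level are assumptions.

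Two stronger readings are not supported. A reader might infer that the test's false-positive rate is in fact above 5% and its intervals in fact too narrow. The documents give no ICC that would establish this, and they specify neither a 5% level nor any interval. A reader might also infer that the pilot could supply the between-group variation needed to size a later group-delivered trial. With two groups, or even four or five, the estimate would be too imprecise for that.

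This is a worthwhile, inexpensive improvement to an exploratory analysis, not a threat to the study's main purpose.

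**What to change.** Amend Section 8.0 as follows, with the ICC range fixed before the outcome data are examined.

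1. Report the mean change in each secondary outcome for each intervention group, beside the pooled mean change.
2. Give the pooled change with a 95% interval whose standard error is multiplied by √[1 + (m − 1) × ICC], at ICC 0, 0.01, 0.05 and 0.10, where m is the number of participants analysed per group. Showing all four lets the reader see how far the conclusion depends on independence.
3. Label any unadjusted paired t test p value as exploratory and as assuming independence between members of the same group.
4. If clearly more than two groups are run, a random group effect with small-sample degrees of freedom may be added. Any ICC estimated from so few groups should be reported as too imprecise to plan a later trial.

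No new data are needed beyond each participant's group. The cost is a short paragraph in Section 8.0, a little more analysis, and wider intervals: at two groups of 10, up to 1.38 times the naive width at ICC 0.10.

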## **3.0 Inclusion/Exclusion Criteria**

Adolescents between the ages of 12-18 years old who are referred for treatment of prediabetes or T2D are eligible for this study. Participants will have normal cognition and will be English speaking as the group is offered in English. Adolescents are not eligible to participate if they have diagnosed cognitive disability that would prevent participation in a group or if they are unable to attend the MBI group sessions.

Criteria for inclusion:

- Age 12-18 years
- Referred to clinic for treatment of prediabetes or type 2 diabetes
- English speaking

Criteria for exclusion:

- Diagnosed cognitive disabilities
- Inability to attend visits due to individual schedules

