## 5.0 Study Procedures

Following enrollment, participants will complete baseline surveys and begin attending the 12-week MBI. Participants will complete surveys following completion of the MBI and at the 12-month follow up. Participants will receive compensation for completing surveys and attending the MBI.

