### Data Collection

**Process Measures:** Intervention fidelity will be assessed with a checklist of session content to ensure that the facilitator is delivering the intervention as intended. Facilitators will follow the manualized curriculum and scripts for mindfulness skills practice.

**Feasibility and Acceptability Measures:** Feasibility and acceptability measures include study participation rate, time to recruit, attendance, study retention rate, study completion rate, data completion, and program acceptability.

**Participant Measures:** Participants will be emailed a link to complete surveys in REDCap. Surveys will be completed at baseline (B), following completion of the MBI at 12-weeks (T1), and at the 12 month follow up (T2). Participants may complete follow-up surveys (12-weeks and 12 months) up to 1 month after the designated time point. A guided interview will also be performed at 12-weeks to receive feedback about the participants' experiences in the study.

Clinical data (HbA1c, BMI, and BMI z-score) will be collected at baseline and at each standard clinical prediabetes or diabetes appointment up to 12 months after the intervention.

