**Table 1. Study Measures**

Feasibility and Acceptability Measures	
Measure	Definition
Study Participation Rate	Number of participants who consented to take part in the study divided by the number of patients approached. We will also document reasons for refusal to participate in the study.
Time to Recruit	Time required to attain the needed sample for each recruitment wave
Attendance	Attendance at each intervention session will be recorded.
Study Retention Rate	Number of participants in a study arm who remain in the study and maintain communication with study staff (regardless of session attendance) divided by the number of participants enrolled in the study.
Study Completion Rate	Number of participants who complete all assessments divided by the number of participants enrolled in the study arm.
Data Completeness	Percentage of questionnaires/study measures completed.
Program Acceptability	Acceptability of the intervention to participants as measured by agreement (on a 5-point likert scale) with different satisfaction measures.

Clinical Measures	
--------------------------	--

Hemoglobin A1c (HbA1c)  
 Body Mass Index (BMI)  
 BMI z-score

*\*When collecting clinical data from prediabetes or diabetes appointments, research team will document any changes to medications that impact glycemia and/or BMI.*

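### Raw BMI and BMI z-score are both tested for change in growing adolescents, neither is given priority, and growth can drive the raw-BMI result over a long follow-up

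*Combined protocol and SAP*

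**What the plan says.** Section 8.0 (Statistical Considerations) sets out the pre/post analysis in one sentence: "A paired t test will be used to compare variables of an individual at baseline and at the end of the study (pre/post". The list that follows is "including HbA1c, BMI, BMI z-score, and survey results". Raw BMI and BMI z-score stand side by side, with no order of priority and no expected-growth value or age adjustment for raw BMI. No significance level is given.

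The eligible ages in Section 3.0 are "Age 12-18 years". There is one arm: in Section 5.0, after enrolment, "participants will complete baseline surveys and begin attending the 12-week MBI". No untreated group estimates growth.

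Under Data Collection in Section 5.0, the clinical values, with both BMI measures among them, "will be collected at baseline and at each standard clinical prediabetes or diabetes appointment up to 12 months after the intervention". Section 8.0 does not tie the end of the study to any of these visits. Table 1 lists both BMI measures without ranking them. Section 2.0, describing how secondary outcomes will give a preliminary view of effect, offers HbA1c and BMI as its examples and does not mention the z-score.

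**The concern.** A paired t test asks whether the mean change is zero. That is a sensible no-effect value only if the variable would stay put without the intervention. BMI in growing adolescents is expected to rise with age, so a group that gained nothing and lost nothing from the programme would still be expected to have a higher mean raw BMI at a late visit. With no control arm, the raw-BMI comparison cannot separate that rise from an effect of the intervention.

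Two misreadings follow. A significant rise could be reported as worsening, or a real reduction relative to expected growth could be missed. Because the z-score is tested as well, the two results can disagree, and the plan does not say which one to believe. Section 2.0 points the reader to raw BMI. The secondary results are meant to inform later trials, so a wrong reading could carry forward.

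**Working it through.** The documents give no power, significance level, growth rate or SD of BMI change, so there is no stated figure to reproduce. The calculation shows how large the problem could be.

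**Inputs from the documents**
- Pairs: n = 20, the completion goal in Section 4.0 (recruitment target 50).
- Null value: mean change of zero, implied by the paired t test in Section 8.0.
- Longest follow-up: 12 weeks (about 3 months) of intervention plus 12 months, or about 15 months from baseline.

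**Inputs assumed (not in the documents)**
- Two-sided significance level 5%.
- Mean rise in raw BMI from growth over 15 months: 0.3 to 0.9 kg/m2.
- SD of individual change: 1.5 to 2.0 kg/m2.

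**Formula.** With mean change m and SD of change s, the paired t statistic is noncentral t with n − 1 = 19 degrees of freedom and noncentrality λ = √n × m / s, where √20 = 4.472. The test rejects when |t| exceeds 2.093.

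**Late endpoint, no intervention effect**

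| Growth (kg/m2) | SD | λ | P(reject) |
|---|---|---|---|
| 0.3 | 2.0 | 0.671 | 9.8% |
| 0.6 | 1.5 | 1.789 | 39.7% |
| 0.9 | 2.0 | 2.012 | 48.0% |
| 0.9 | 1.5 | 2.683 | 72.1% |

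Nearly all of these rejections are in the direction of a rise. Even in the first row, 9.3 of the 9.8 percentage points are.

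**Endpoint at 12 weeks, no intervention effect.** Taking growth in proportion to time, 3/15 of 0.3 to 0.9 is 0.06 to 0.18 kg/m2.

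| Growth (kg/m2) | SD | λ | P(reject) |
|---|---|---|---|
| 0.06 | 2.0 | 0.134 | 5.2% |
| 0.18 | 1.5 | 0.537 | 8.0% |

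This is close to the nominal 5%, so the undefined endpoint largely decides whether the problem matters.

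**Masking.** Suppose the intervention truly lowers BMI by 1.0 kg/m2 relative to expected growth (also an assumption), with s = 2.0 and n = 20.
- No growth: m = −1.0, λ = −2.236, chance of a significant fall 56%.
- Growth 0.3: m = −0.7, λ = −1.565, chance 32%.
- Growth 0.9: m = −0.1, λ = −0.224, chance 4%.

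**Larger samples do not help.** With growth of 0.5 kg/m2 and SD 2.0, the chance of a significant rise with no intervention effect is 18% at n = 20 and 41% at n = 50.

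**The case against.** The strongest reply is that the sentence at issue also tests BMI z-score, so a growth-standardised result will sit beside the raw one. That stands. The remaining gap is that neither measure is ranked and that Section 2.0 mentions only raw BMI.

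Second, a follow-up of a year or more is an interpretation. Section 8.0 names no visit, and about 15 months is a maximum because clinical values come from routine appointments. A late endpoint is the more natural reading, but at 12 weeks the effect is small.

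Third, growth and SD are assumed, so the 10% to 72% range illustrates the issue and does not estimate it for this trial. Participants near 18 may grow less.

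Fourth, BMI is a secondary, exploratory outcome. No success criterion or go/no-go rule depends on it, and the primary feasibility and acceptability conclusions are untouched. This stands and lowers the priority.

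A reader might infer more: that the raw-BMI test is biased toward worsening whatever the intervention does, or that the sponsor collects the z-score because it knows raw BMI is unsuitable. The documents support neither. Participants are under clinical care, and Table 1 provides for recording medication changes that affect BMI, so the net drift could go either way. The plan gives no reason for including the z-score. Nor is a significant rise in raw BMI a false statement about the pre/post change; the error would lie in attributing it to the intervention.

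**Conclusion.** The point holds in a limited form and is minor. Section 8.0 tests raw BMI against zero change in a single arm of adolescents, alongside BMI z-score and without ranking the two. At a late endpoint, and under the assumed growth and SD, the nominal 5% test would reject in about 10% to 72% of trials with no intervention effect; at 12 weeks, in about 5% to 8%. These figures also assume 20 pairs, a two-sided 5% level and no net BMI change from concurrent care.

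It would go too far to conclude that moving to the z-score makes the result causal. It removes expected growth, but concurrent care, medication changes and other time effects remain. Without a control arm, a change in z-score cannot be attributed to the intervention either.

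**What to change.** In Section 8.0:
- name change in BMI z-score as the BMI outcome for inference;
- report raw BMI descriptively at each time point, without a test;
- state which visit, with what window, supplies the end-of-study value.

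In Section 2.0, align the example of clinical measures by naming BMI z-score.

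The cost is a few words in two sections and the loss of one exploratory test on the raw scale. No new data, visits or participants are needed, since the z-score is already collected and already in the test list.

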## **9.0 Privacy/Confidentiality Issues**

Research material obtained from living human subjects will include medical records, with medical information collected by the PI/research team during screening and study visits, as well as data collected from surveys.

Data will be stored in IU REDCap, a secure web platform used to support academic research and is compliant with local and federal regulations for data security and integrity. Access to the study data will be restricted to study personnel.

Any paper records containing identifying information will be kept in locked files accessible only to study staff and unlocked only while a study staff member is physically present. All computer records will require password access; computer workstations will be locked when unattended.

